# Section 6. GENERAL POINTS FOR STATISTICAL ANALYSIS

### 6.1. GENERAL METHODS

All statistical analyses as covered by this SAP will be performed using two different programming languages, for example, R version 3.4.1 or later [6], Python version 3.11 or later [7], or SAS® version 9.4 or later [8] as a diverse self-checking pair.

Summary statistics for continuous variables will be:

- Number of non-missing observations
- o Mean and standard deviation
- o Median
- First and third quartiles
- o Minimum and maximum
- Number of missing observations

Categorical variables will be summarized as counts and percentages of appropriate total, with 'missing' as an additional category.

#### 6.2. DECIMAL PLACES

- The mean and median, as well as the first and third quartiles for a set of values, will be presented to 1 more decimal place than the original values.
- Standard deviations and confidence interval limits will be presented to 2 more decimal places than the original values.
- The minimum and maximum will report the same number of decimal places as the original values.
- Percentages will be displayed with 1 decimal place. Percentages will not be presented when the count is zero, and 100% will be presented with no decimal place. Note that for categorical data, the number of missing observations will be included in the calculations.
- P-values will be displayed with 3 decimal places.

#### 6.3. WITHDRAWALS AND MISSING DATA

A randomized subject will be taken as having withdrawn from the study if, with regards to the 'study exit' CRF, the question 'Did the subject successfully complete the study?' is answered 'no'.

A subject will be taken to have completed the study if the answer to the 'study exit' CRF question 'Did the subject successfully complete the study' is 'yes'.

See Section 4.1 for the handling of missing data for the primary endpoint.

See Section 4.2 for the handling of missing data for the key secondary endpoint.

Each of the baseline covariates included in the NPANCOVA method have rules to impute any missing values, and these are described in Section 8.2.1.3.

Incomplete values of 'date stopped smoking' will also be imputed. The rules are:

- Day is imputed as the 15th day of the given month if only day missing e.g. 'July 2000' becomes '15th July 2000'
- $\circ~$  Day and month will be imputed as 1st July if day and month are missing e.g. '2000' becomes '1st July 2000'

# Section 7. DISPOSITION AND BASELINE CHARACTERISTICS

The following variables will be summarised i.e. listed and/or tabulated by treatment group across the indicated population. Each section corresponds to a different table and/or listing and to either a single CRF or a combination of one or more CRFs. For details of the summaries, see the table shells and listings.

Categorical variables will be accompanied by possible values and '(Free text)' means the variable is categorical but the category is entered as free text by the study administrator. Otherwise, it will be assumed the variable is continuous. See Section 5: General Methods for the manner in which each variable type is summarised.

Note: These summaries will only be produced at the end of the study i.e. not the interim analysis.

## 7.1. INFORMED CONSENT

The following will be summarised over all screened subjects:

- Screening date (format of visit)
- Informed consent given (yes, no)
- o Date of informed consent

#### 7.2. SUBJECT DISPOSITION AND WITHDRAWAL

The following will be summarised in tabular form:

- o Number of screened subjects
- o Number of subjects who are screen failures
- Number of subjects Randomized
- o Number of randomized subjects who completed the study
- Number of randomized subjects who did not complete the study, by reason (if more than one reason for a subject, count all reasons):
  - Screen failure
  - Progression to moderate or severe COVID-19
  - Pregnancy
  - (Serious) adverse event
  - Death
  - Protocol Deviation
  - Withdrawal by subject
  - Withdrawn at investigator's discretion
  - Termination of the study
  - Device deficiency
  - Lost to follow-up
  - Other

- Number of subjects in the FAS
- Reason(s) for subject exclusion from the FAS
  - Subject mis-randomized
  - Subject ID corresponds to study participant that was re-randomized under a different subject ID
- Number of subjects in Safety population
- Number of subjects in PP population
- Reason(s) for subject exclusion from the PP population (if more than one reason for a subject, include all reasons)
  - Received the wrong treatment
  - Subject not positive for COVID-19 based on qPCR
  - Did not satisfy Inclusion criterion #1
  - Did not satisfy Inclusion criterion #3
  - Did not satisfy Inclusion criterion #4
  - Satisfied exclusion criterion #2
  - o Satisfied exclusion criterion #4
  - Number of treatments received was <7
  - After randomization received one or more FDA-approved medications for COVID-19 treatment.

All summaries will be provided by treatment group and percentages will be based on the number of subjects randomized to the treatment group, except for counts related to subjects screened or screen failures.

#### 7.3. INCLUSION CRITERIA, EXCLUSION CRITERIA, PROTOCOL DEVIATIONS

Inclusion criteria not met, exclusion criteria met, and other Protocol Deviations will be summarised for all randomised subjects.

In addition, a listing will be produced including the following information for the FAS:

- o Date of deviation
- o Applicable study day
- Deviation category (inclusion/exclusion criteria, informed consent,...)
- Related to COVID-19 restrictions (Yes, no)
- Deviation pre-approved by sponsor (Yes, no)
- Type (major, minor)

#### 7.4. E-DIARY TRAINING AND DEVICE

The following will be summarised over the FAS:

- E-diary training completed (yes, no)
  - If yes: date

- If no: reason
- o RD-X19 device provided to the subject (yes, no)
  - If yes: date
  - If no: reason
- Device to which randomised
- o Device returned at study end

Device to which randomized can be found in the question 'Randomization outcome' in the 'Randomization Assignment' CRF.

Device returned can be found in 'Device ID' field in the 'RD-X19 Device Collection' with a list of which devices are active and which are sham.

## 7.5. DEMOGRAPHIC DATA

The following will be summarised in tables and listings for the FAS:

- Age at time of consent (continuous variable)
- Age category at time of consent (40-49, 50-59, 60-64, ≥65)
- Sex (male, female, undifferentiated, unknown)
- o Weight (kgs),
- o Height (m)
- o BMI (kg/m^2)
- BMI category (< 18.5 ='underweight';  $\geq 18.5$  to <25 ='healthy weight';  $\geq 25$  to <30 ='overweight';  $\geq 30$  to <40 ='obese';  $\geq 40 =$ `morbidly obese`).
- Ethnicity (Hispanic or Latino, not Hispanic or Latino, not reported, unknown)
- Race (American Indian, Alaska Native, Asian, Black, African American, Native Hawaiian or Pacific Islander, White, Two or more races, Not reported, Unknown)

# 7.6. BASELINE COVID-19-RELATED INFORMATION AND OTHER BACKGROUND CHARACTERISTICS

The following variables will be summarised in tables for the FAS.

- Result of baseline SARS-Cov-2 antigen test (positive, negative, inconclusive)
- SARS-Cov-2 antigen test type (Flowflex, BinaxNOW)
- o Result of flu A rapid antigen test (positive, negative, invalid)
- Result of flu B rapid antigen test (positive, negative, invalid)
- Randomization Stratum (age 40-49, Disease Severity Score < 1.25; age 40-49, Disease Severity Score ≥ 1.25; age ≥50, Disease Severity Score < 1.25; age ≥50, Disease Severity Score ≥ 1.25)

- Total baseline disease severity score (continuous variable)
- Total baseline disease severity score (<1.0,  $\geq$ 1.0-<1.25,  $\geq$ 1.25-<1.75,  $\geq$ 1.75)
- Baseline individual self-assessed symptom scores:

- Cough (0,1,2,3)
- Sore throat (0,1,2,3)
- Nasal congestion (0,1,2,3)
- Headache (0,1,2,3)
- Chills or sweats (0,1,2,3)
- Myalgia (0,1,2,3)
- Fatigue (0,1,2,3)
- Nausea, with or without vomiting (0,1,2,3)
- Loss of taste (yes, no)
- Loss of smell (yes, no)
- Baseline oral temperature (continuous variable)
- o Baseline oral temperature (<100.5, ≥100.5 °F)
- Baseline heart rate beats/min (continuous variable)
- Baseline heart rate (<70, ≥70-<80, ≥80-<90, ≥90)

- Systolic blood pressure (mmHg)
- Diastolic blood pressure (mmHg)
- Oxygen saturation at rest (%)
- Respiratory rate at rest (continuous variable)
- o Respiratory rate at rest (<20, ≥20 breaths/min)
- Oxygen saturation from Dyspnea on exertion assessment (%)
- Respiratory rate from Dyspnea on exertion assessment (continuous variable)
- Respiratory rate ≥20 and Oxygen saturation <96% from Dyspnea on exertion assessment (yes, no)
- Hours at screening since onset of first COVID-19 sign or symptoms (continuous variable)
- Hours at screening since onset of first COVID-19 sign or symptoms ( $\leq 24$ ,  $>24-\leq 48$ ,  $>48-\leq 72$ , >72)
- Baseline Risk Factor Score (as defined in Section 8.2.1.3)
- Baseline Log10 Nasopharyngeal Viral Load category (Not Detected or Below LLOQ; Above ULOQ; Numerical value between LLOQ and ULOQ, missing)
- Baseline Log10 Nasopharyngeal Viral Load (summary statistics [copies/mL] for numerical value between LLOQ and ULOQ)
- Result of SARS-Cov-2 qPCR test (positive, negative). Note: Any sample with detectable SARS-CoV-2 RNA will be classified as a "positive" qPCR test result, even if the viral load is below the assay's lower limit of quantitation or if the result is "inconclusive". Any other result will be classified as a "negative" qPCR test result.
- SARS-Cov-2 variant identified by qPCR (frequency distribution)
- COVID-19 Vaccination status (yes, no)
- Number of COVID-19 vaccinations received (frequency distribution)
- Previous COVID-19 diagnosis via FDA-approved diagnostic test (yes, no)
- Significant risk of exposure to COVID-19 over the past two weeks (yes, no)
- Type of exposure (commercial flight, major sporting event, contact with someone with COVID-19, other) (use COVID-19 risk of exposure subform)

# 7.7. MEDICAL HISTORY

The following will be summarised in listings for the FAS, and categorical variables as well as all details on Smoking history will also be summarized in tables:

- History of substance abuse (never, current, former)
  - If current or former: years of substance abuse, specify substance, use in last month
  - If former: years since stopped
- Drinking history (never, current, former)
  - If current or former: years of drinking, units per day, history of alcohol intoxications (yes, no)
  - If former: years since stopped
- Smoking history (never, current, former)
  - If current or former: years of smoking (summary statistics), cigarettes per day (summary statistics)
  - If former: years since stopped (>0-≤2, >2-≤10, >10)
- History of asthma (yes, no)
  - If yes: start date, end date/ongoing
- History of vasomotor rhinitis (yes, no)
  - If yes: start date, end date/ongoing
- History of hypersensitivity or severe allergic reaction to sun exposure?
  - If yes: start date, end date/ongoing
- Frequent and recurring presence of oral diseases/conditions? (yes, no)
  - If yes: start date, end date/ongoing
- Other significant medical history

#### 7.8. PREGNANCY TESTING

The following variables will be summarized in listing form for the FAS.

The following will be taken from the 'Pregnancy test' CRF:

• Is subject of childbearing potential (yes, no)

- If no: reason (post-menopausal, surgically sterile, other)
- If yes: was a pregnancy test performed (yes, no)
  - If yes: date of test, result (positive, negative, invalid)

### 7.9. BASELINE MEDICATIONS AND THERAPIES

The following will be summarised within tables for the FAS:

- Medications/vitamins/supplement/therapies taken in the 30 days prior to screening and not ongoing at time of screening (yes, no)
- Concomitant medications/vitamins/supplement/therapies ongoing at time of screening (yes, no)
- History of use of any FDA-authorized treatment for COVID-19? (yes, no)
- History of any systemic antiviral therapies? (yes, no)
- History of oral or parenteral corticosteroid use, including use of nasal or inhalable steroids? (yes, no)
- History of any chronic medical condition that has required adjustments to the type, dose or schedule of medical treatments? (yes, no)
- Requirement to use narcotic medication for analgesia? (yes, no)

# Section 8. ANALYSIS OF STUDY ENDPOINTS

## 8.1. INTERIM ANALYSIS

A blinded sample size review will be carried out by an independent statistician based on the first 164 randomized subjects after the last of these subjects has reached the Day 14/ET visit.

The pooled proportion ( $p_{obs}$ ) of subjects with an event for the primary endpoint (sustained resolution of COVID-19 signs and symptoms without subsequent symptom recurrence or disease progression) will be determined, and if this is less than 0.70 then, in order to obtain approximately 228 such events at the end of the study, the total number of randomized subjects will be increased to:

$$326 \times \frac{0.70}{p_{obs}}$$

(rounded up to the next multiple of two, due to the 1:1 active:sham randomization) subject to a cap of 380.

The number of randomized subjects will not be decreased, and no unblinded assessment of efficacy will be carried out at this time.

A table will be produced summarizing this analysis. It will include:

- The number of randomized subjects on which the analysis is based
- The pooled proportion of subjects with sustained COVID-19 resolution
- The new number of randomized subjects for the study
- The change (increase only) from the original number

No other listings or tables will be produced as part of the interim analysis. A copy of the data used to undertake the interim analysis will be kept and archived.

## 8.2. PRIMARY ENDPOINT

All analyses of the primary endpoint will be carried out only after implementing all data handling rules described in Section 4.1.

All primary analysis for this endpoint will be based on the FAS.

Event times and censoring status will be listed; the censoring status will additionally be tabulated. The following rules for event times and censoring will be implemented in the analysis of the primary endpoint:

- I. Subjects that are hospitalized will be censored at 360 hours, which corresponds to the end of the time window for the day 14 visit. This rule takes precedence over all other rules.
- II. A subject that records "SSSSS" i.e., five consecutive timepoints (corresponding to an approximately 48-hour period) at which the signs and symptoms have resolved who does not have any subsequent symptom recurrence or subsequent disease progression during the subject's remaining time on study, will have the event at the time of the first "S" in this sequence.
- III. A subject not satisfying case (i) or (ii), who takes nirmatrelvir/ritonavir or molnupiravir after initiating study treatment will be censored at the time that they first took this antiviral medication.
- IV. Subjects not satisfying case (i), (ii), or (iii) will be censored at the last time that they have e-diary data recorded.
- Note: Subjects taking nirmatrelvir/ritonavir or molnupiravir after initiating study treatment must have recorded "SSSSS" (or equivalent) prior to starting this antiviral medication to be counted under case (ii), and if not then they will be counted under case (iii).
- Note: The CRF only records the date that a concomitant medication is started, and does not record the time. Therefore, for subjects in case (iii) the time of censoring will be taken as midday. However, if any case (iii) subjects started the medication on the day of randomization then the censoring time will be the latter of midday or the time of randomization.

For all analysis, the covariates adjusted for/covariates in any models are included in a footnote to any related tables or figures.

Counts and percentages will also be provided in the tables reporting NPANCOVA analyses for subjects, which in the notation of Section 8.2, are in each of cases (i), (ii), (iii), and (iv).

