- 3) Those who progress to moderate disease indicated by new onset shortness of breath (respiratory rate ≥20/minute) and SpO2 of < 96% confirmed by pulmonary imaging or lower airway disease diagnosed by pulmonary imaging involving < 50% of lung parenchyma;

- Those who progress to severe disease with respiratory rate >30/minute and/or O2 saturation ≤93% on room air or lower airway disease confirmed by pulmonary imaging involving ≥ 50% of lung parenchyma;
- 5) Those who require hospitalization for severe COVID-19;
- 6) Those who require endotracheal ventilation or ECMO with or without the use of solumedrol; and
- 7) Those who die.
- Subjects with a primary care, urgent care, or emergency room visit that are not hospitalized as a result of their medical consultation, may continue treatment with the investigational device and should attend regularly scheduled follow up visits per protocol. Subjects that are admitted to the hospital should discontinue all treatment in lieu of standard of care for severe/critical COVID-19 illness or other SAEs. Such subjects' endpoint data will be right censored as specified in the Statistical Analysis Plan (SAP).
 - Subjects who are treated with any FDA-authorized COVID-19 therapy will discontinue treatment but will continue to be followed per protocol. Such subjects' endpoint data will be right censored as specified in SAP.
 - Subjects who first reach clinical resolution on or after study day 11 should be scheduled for their day 14 visit, which has a +/- 2 day window, so that a total of five consecutive visits (including the first resolution visit) are captured where resolution *may* be observed thus allowing the primary clinical sustained resolution endpoint to be met. Under no circumstances, however, may a study subject be scheduled for their day 14 visit beyond study day 16.

	Page 46 of 70
EmitBio Inc.	Version: 3.1
EB-P30-01	7 February 2024

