- (ii) A subject that records "SSSSS" i.e., five consecutive timepoints (corresponding to an approximately 48-hour period) at which the signs and symptoms have resolved who does not have any subsequent symptom recurrence or subsequent disease progression during the subject's remaining time on study, will have the event at the time of the first "S" in this sequence;

	Page 55 of 70
EmitBio Inc.	Version: 3.1
EB-P30-01	7 February 2024

- (iii) A subject not satisfying case (i) or (ii), who takes nirmatrelvir/ritonavir or molnupiravir after initiating study treatment will be censored at the time that they first took this antiviral medication; and
- (iv) Subjects not satisfying case (i), (ii), or (iii) will be censored at the last time that they have e-diary data recorded.
- Note: Subjects taking nirmatrelvir/ritonavir or molnupiravir after initiating study treatment must have recorded "SSSSS" (or equivalent) prior to starting this antiviral medication to be counted under case (ii), and if not then they will be counted under case (iii).

Further details on data handling rules will be provided in the SAP.

Supportive analyses for each of the methods described in this section will also be carried out for the PP population. Further sensitivity analyses for the primary endpoint will be described in the SAP.

Analyses of the Key Secondary Endpoint

At each of the twice-daily assessment times at which the subject is scheduled to take the SARS-CoV-2 antigen test the results will be either Negative (N), Positive (P), Inconclusive (I) or Missing (M).

The first step in defining the key secondary endpoint is to identify cases that will be counted as having "two consecutive negative SARS-CoV-2 antigen tests". The following sequences will be counted as satisfying this condition: (a) "NN" and the two tests are at least six hours apart; (b) multiple consecutive "N" values where the first and last must be at least six hours apart; or (c) "N" followed by up to three "M" or "I" values followed by "N" where the two "N" values must be at least six hours apart. In the remainder of Section 9.4.1.3 the use of "NN" will be refer to any of cases (a)-(c).

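### The primary-endpoint censoring rule covers only nirmatrelvir/ritonavir and molnupiravir, while Protocol 8.6 and 8.1.3 call for right censoring after FDA-authorized COVID-19 therapy generally

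*SAP*

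**What the plan says.** Protocol 8.6 defines the intercurrent event broadly: "Subjects who are treated with any FDA-authorized COVID-19 therapy will discontinue treatment but will continue to be followed per protocol". It adds that such subjects' "endpoint data will be right censored as specified in SAP". Protocol 8.1.3 likewise says that FDA-authorized therapies for progressed COVID-19 lead to right censoring for efficacy. That section gives the two named antivirals as examples of drugs known to treat COVID-19, not as a closed list.

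The operative rules for the primary endpoint are in SAP 8.2:

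- Rule I: "Subjects that are hospitalized will be censored at 360 hours, which corresponds to the end of the time window". It overrides all other rules.
- Rule II: SSSSS with no later recurrence or progression is an event at the first S.
- Rule III: a subject outside I and II "who takes nirmatrelvir/ritonavir or molnupiravir after initiating study treatment will be censored at the time that they first took this antiviral medication".
- Rule IV: everyone else "will be censored at the last time that they have e-diary data recorded".
- Note: users of the two named drugs must have reached SSSSS before starting the drug to count under rule II.

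Protocol 9.4.1 gives the same four rules and the same Note.

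Two analyses use the wider class of any FDA-authorized COVID-19 treatment, with censoring at 360 h: the sensitivity analysis in SAP 8.2.5, and the key secondary endpoint (Protocol 9.4.1 rule (i), SAP 8.3.1). The Kaplan-Meier, Cox and subgroup analyses of the primary endpoint state no separate rule, so they share the narrow one.

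**The concern.** The same clinical event, authorized therapy started and device stopped, is handled differently in the primary analysis according to the drug's name. For the two named antivirals, recovery after intake is not credited to the randomized device. For any other authorized therapy it is.

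The plan foresees treatment without admission. Protocol 4.3 sends subjects who progress to moderate disease to primary or urgent care. Protocol 8.6 also provides for outpatient attendance; for example, those with an "emergency room visit that are not hospitalized as a result of their medical consultation, may continue treatment with the investigational device". Protocol 4.1 names antibody therapies and convalescent plasma, besides antivirals, as therapies studied in non-hospitalized people and authorized for those at increased risk.

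At stake is whether a few subjects count as events in the primary analysis of a pivotal trial. If the conflict were noticed only after unblinding, settling it would be a post hoc choice about the primary endpoint.

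**Working it through.** **Rule trace.** Take a non-hospitalized subject who starts an authorized therapy other than the two named drugs before any SSSSS.

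| Later course | SAP 8.2 as written | Protocol 8.6 | SAP 8.2.5 |
|---|---|---|---|
| SSSSS, no later recurrence or progression | Event at first S (rule II; the Note does not apply because the drug is not named) | Right censored, time left to the SAP | Censored at 360 h |
| Never SSSSS | Censored at last e-diary entry (rule IV) | Right censored, time left to the SAP | Censored at 360 h |

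Earlier progression does not block the event, since rule II bars only progression after SSSSS.

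**Per-protocol analysis.** Reason 6 in SAP 5.3 excludes recipients of FDA-approved COVID-19 medication. It keeps those first treated after Urgent Care, Emergency Room or hospital care, provided reasons 1-4 do not apply and at least one treatment was received. Subjects first treated through primary care stay excluded. The PP analysis therefore removes part of the group.

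**The plan's own figures.** Inputs from SAP 3.3: one-sided alpha 0.025, 1:1 allocation, N = 326, 228 events.

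- Schoenfeld: events = 4(z_alpha + z_beta)² / (ln HR)². HR 0.62 at 95% power: 4 × (1.960 + 1.645)² / 0.478² gives 228. HR 0.65 at 90% gives 227, and HR 0.69 at 80% gives 229.
- Power with 228 events: 95.0%, 90.2% and 80.0%.
- Expected events: 163 × 0.90 + 163 × 0.50 = 228.2.

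All agree with the plan.

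**Events at risk.** The documents give no rate of use, so f is an assumption. If a share f of all subjects takes another authorized therapy before SSSSS and would otherwise be events at the pooled 0.70, widening the rule removes 326 × f × 0.70 events: 2.3 at f = 1% and 11.4 at 5%. Power at HR 0.65 falls from 90.2% to 89.9% and 88.7%.

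**Effect on the hazard ratio.** The check simulated 6,000 trials per scenario with 163 subjects per arm, exponential times and pooled 70% events by 312 h. HR is Sham versus RD-X19. At HR 0.65 the arm event rates are 77.7% (RD-X19) and 62.3% (Sham), since 0.223^0.65 = 0.377; the plan's 90%/50% split was not used. Assigned users start therapy at a uniform time between 24 and 168 h if unresolved, and their resolution hazard then doubles. Each trial was analysed by a Cox model under both rules.

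| Assigned use, Sham / RD-X19 | HR as written | HR, wider rule | Difference |
|---|---|---|---|
| 1% / 1% | 0.650 | 0.650 | 0.000 |
| 2% / 2% | 0.652 | 0.651 | +0.001 |
| 5% / 5% | 0.652 | 0.650 | +0.002 |
| 2% / 1% | 0.655 | 0.652 | +0.003 |
| 1% / 2% | 0.645 | 0.647 | -0.002 |
| 5% / 2.5% | 0.658 | 0.650 | +0.008 |
| 2.5% / 5% | 0.644 | 0.649 | -0.005 |

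Assigned users who resolve first never start therapy, so actual use is lower. At 1% assigned, 1.8 events plus 0.4 never-resolved users out of 326 is 0.7%. At 5%, (9.0 + 2.2)/326 = 3.4%. The two rules give a different significance decision in 1.0% (1% assigned) to 2.4% (5% assigned) of trials. Never-resolved users are censored about 210 h later than intake under rule IV. With hazard factors 1 and 3 at 2%/2% use, the HRs are 0.649 vs 0.649 and 0.650 vs 0.648.

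**The case against.** The strongest reply is that the documents show no affected patient. The antivirals Protocol 4.1 names for outpatients are the two in rule III. It adds that immune-based therapies are intravenous, that authorizations are restricted to people at increased risk, and that new variants resist antibodies. Hospitalized subjects already fall under rule I. This stands as a limit on size, but Protocol 4.1 does name other therapy classes, so the group cannot be assumed empty.

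Second, Protocol 8.6 defers to the SAP, and SAP 8.2 agrees with Protocol 9.4.1, so the operative derivation is unambiguous. A reader might infer that Protocol 8.6 alone yields competing event times. It does not, because it gives no censoring time. But the deferral settles how to censor, not whether, and SAP 8.2 gives some of these subjects an event.

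Third, SAP 8.2.5 repeats the primary NPANCOVA with the wider class and reports the users separately. That is real cover, though partial. It also moves censoring to 360 h, adds censoring for progression, and overrides an SSSSS reached before therapy. A difference from the primary result could not be put down to drug class, and the primary p-value keeps the narrow rule.

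**Conclusion.** The mismatch is real and minor. It lies within the protocol, between 8.6 and 8.1.3 on one side and 9.4.1(iii) on the other, and the SAP follows 9.4.1.

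Its size rests on assumed rates of use, start times and hazard factor. With actual use of about 0.7% to 3.5%, the HR changes by about 0.002 or less with equal use and by up to about 0.008 with unequal use, in a direction that depends on which arm uses more.

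A reader might infer that the rule biases the trial towards the device or threatens its conclusion. The documents do not support that: they give no use by arm, and in the simulation heavier Sham use moves the HR towards 1. Nor do they support reading every other analysis as using the wider class, or the PP analysis as leaving the whole group in.

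**What to change.** In SAP 8.2 rule III and its Note, and in Protocol 9.4.1(iii) and its Note, replace the two drug names with *any FDA-authorized or FDA-approved COVID-19 treatment*. Keep censoring at first intake, the midday convention, and the condition that SSSSS must precede the therapy. Fix the list of qualifying treatments from the coded concomitant medications before unblinding. Keep SAP 8.2.5 as the sensitivity analysis; its different censoring time of 360 h remains.

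The cost is wording only. SAP 8.5.2 already lists generic name, drug code and start date, SAP 8.2.5 and 8.3.1 already need these users identified, and SAP 2.1 allows amendment before database lock. The downside is that a few more subjects are censored at intake. In the simulation this loses about 2 events at 0.7% actual use and 9 at 3.4%, and it relies slightly more on non-informative censoring.
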